4.4 Safety Objectives

To evaluate the safety and tolerability of AK002 in adult and adolescent subjects with active EoE by determining AE incidence and severity, study withdrawals due to AE, changes in vital signs and laboratory tests including immunogenicity, changes in concomitant medications beginning on or after the first infusion of study drug, and other safety parameters.

4.5 Target of Estimation

The estimand (target of estimation) for the study is:

In patients with active EoE, what is the between group (AK002 vs. Placebo) difference in the proportion of tissue eosinophil responders at Week 24, and between group difference in DSQ from baseline to Weeks 23–24 as measured by the patient-reported outcome (PRO) Dysphagia Symptom Questionnaire.

The sections below describe the attributes of the estimand consistent with the ICH E9 Addendum (FDA, 2021).

4.5.1 Population Targeted by the Scientific Question

The population targeted by the scientific question is defined by the inclusion and exclusion criteria as part of the study protocol. Patients must have a clinical diagnosis of active EoE.

4.5.2 Variables of Interest (or Endpoint) Required to Address the Scientific Question

The co-primary endpoints to be obtained for each subject in this study to address the scientific question are Tissue Eosinophil Responders at Week 24 and change in DSQ from Baseline to Weeks 23–24 as measured by the PRO questionnaire.

4.5.3 Treatment

AK002 or placebo administered to subjects on Days 1, 29, 57, 85, 113, and 141.

4.5.4 Intercurrent Events

The events below are considered intercurrent events (ICE) confounding with the efficacy outcomes.

- Premature discontinuation from the study.
- Use of prohibited/restricted medication.
- Any therapeutic EGD (defined as dilatation or other intervention for a narrowing or stricture of the esophagus) at any point during the study through Week 24.

Intercurrent events are described above, and further clarification and handling of ICE including prohibited/restricted medications are detailed in the Statistical Analysis Plan (SAP).

4.5.5 Strategy for Handling Intercurrent Events

For analysis of the study product, the estimand tissue eosinophil values and DSQ scores will be counted as non-responders for binary variables and set to missing for continuous outcomes from the point when an ICE occurs. An appropriate method for handling missing data through statistical modeling (e.g., multiple imputation [MI]) will be used. The estimand will provide an answer to the question that is crucial to individual subjects:

If I take this study medication as part of my treatment regimen, without adding any further medications that may impact the underlying disease or exit the study prematurely, what improvements in histology and PRO symptoms might be anticipated after 24 weeks?

4.5.6 Summary Measure of the Estimand

- Percent (and 95% confidence interval [CI]) of subjects having tissue eosinophil response at Week 24 in the AK002 and placebo treatment groups and the absolute difference (and 95% CI) in the percent response between treatments.
- Least squares mean (LSM) (and standard error [SE]) of change from baseline to the DSQ of Weeks 23-24 and the between treatment difference in the AK002 and placebo treatment groups LSM.

5. Study Design

5.1 Study Overview

This is a Phase 2/3, multicenter, randomized, double-blind, placebo-controlled study to evaluate the safety, tolerability, and clinical benefit of AK002 in adult and adolescent subjects with active EoE. Subjects enrolled in the study will receive 6 infusions of placebo or AK002 administered every 4 weeks and will be followed for 8 weeks after the last dose.

Subjects who successfully complete the double-blind, placebo-controlled treatment period (including the Day 169 visit) may have the option to receive 6 doses of open-label AK002 through participation in the optional Open-Label Extended Dosing (OLE) Period of the study and will be followed for 8 weeks after the last dose.

Subjects will be consented and then screened for 14 to 60 days (or a maximum of 35 days after the Screening EGD, whichever is shorter). During the screening period, a baseline, stable regimen of PPI and/or dietary intake will be established, if needed, and baseline disease activity data will be collected. Swallowed topical corticosteroids and systemic corticosteroids will not be allowed. Subjects who meet eligibility criteria can be enrolled into the study. Subjects who do not meet all eligibility criteria at screening, or who qualify at screening but are not enrolled, may be assigned a new patient identification number and rescreened once. Subjects rescreened within 30 days of signing the initial informed consent form (ICF) will not need to re consent if no changes have been made to the ICF.

Prior to the first dose of study drug (12–24 hours prior to the infusion), subjects will be premedicated with oral prednisone (40 mg if body weight is <40 kg, 60 mg if body weight is \geq 40 kg and <60 kg, or 80 mg if body weight is \geq 60 kg). Subjects will self-administer oral prednisone 12–24 hours prior to the start of the first infusion only.

Eligible subjects will receive the first dose of placebo or AK002 (1 mg/kg) on Day 1 and will remain confined to the clinic for at least 1 hour of observation (or greater, as per Investigator discretion) following the end of the infusion. On Day 29, subjects will receive a second dose of placebo or AK002 (1 mg/kg or 3 mg/kg) and will remain confined to the clinic for at least 1 hour of observation (or greater, as per Investigator discretion) following the end of the infusion. If the study drug is well tolerated (no stopping rules met), subjects will continue to receive doses of placebo, 1 mg/kg AK002, or 3 mg/kg AK002 on Days 57, 85, 113, and 141 for a total of 6 doses. Subjects will remain at the site for at least 1 hour of observation (or longer, as per the Investigator's discretion) after each dose. In the event of an IRR, the subject may require prolonged observation (>1 hour or until the symptoms resolve), as per the Investigator's discretion. Subjects will also be instructed to immediately contact the study doctor if any reactions occur after discharge.

During the treatment period, subjects will return to the clinic for study visits as described in the Schedule of Events ([Table 1](#)). After completion of the Day 169 visit, the Investigator will evaluate whether the subject is eligible for the OLE period. Only subjects who successfully complete the double-blind treatment period (including the Day 169 visit) will have the option to participate in the OLE period, provided all eligibility criteria for the OLE period are satisfied.

Subjects who are not eligible for (or who choose not to participate in) the OLE period will complete the Follow-Up Period, including the Day 169 (± 7) visit (4 weeks after the last dose) and the Day 197 (± 7) visit (8 weeks after the last dose) per the Schedule of Events (Table 1).

Eligible subjects who choose to participate in the OLE period will begin following the OLE Schedule of Events (Table 5) and will receive the first dose of open-label AK002 approximately 1 week after Day 169 (on Day 176 ± 3 days).

If absolute lymphocyte and/or eosinophil counts have not recovered (to normal range or baseline levels) by the Day 197 visit (or the Day 372 visit for subjects participating in the OLE period), extended follow-up visits are required approximately every 4 weeks to monitor blood counts until they recover.

The study design is summarized as follows:

- A 14 to 60-day (or a maximum of 35 days after the Screening EGD, whichever is shorter) screening period with baseline evaluations for eligibility, including baseline disease activity (by daily PRO questionnaire) and esophago-gastro-duodenoscopy (EGD) with biopsy.
- Prior to the first dose of study drug (12–24 hours prior to the infusion), subjects will be premedicated with oral prednisone (40 mg if body weight is < 40 kg, 60 mg if body weight is ≥ 40 kg and < 60 kg, or 80 mg if body weight is ≥ 60 kg).
- Eligible subjects will receive 6 doses of AK002 (or placebo) by IV infusion on Days 1, 29 (± 3), 57 (± 3), 85 (± 3), 113 (± 3), and 141 (± 3). Subjects will self-administer prednisone 12–24 hours prior to the start of the first infusion only.
- Subjects will remain at the site for at least 1 hour of observation after each dose. In the event of an IRR, the subject may require prolonged observation (> 1 hour or until the symptoms resolve), as per Investigator discretion. Subjects will also be instructed to immediately contact the study doctor if any reactions occur after discharge.
- A repeat EGD with biopsy will be performed on Day 169 (± 3) or 28 (± 3) days after last dose if subject is terminated early between Day 29 and Day 169 study visits.
- After completion of the Day 169 visit, the Investigator will evaluate whether the subject is eligible for the OLE period.
- Subjects who are eligible and choose to participate in the OLE period will begin following the OLE Schedule of Events (Table 5) on Day 176 (± 3). The OLE period includes 6 doses of open-label AK002 administered on Days 176 (± 3), 204 (± 3), 232 (± 3), 260 (± 3), 288 (± 3), and 316 (± 3) and post-treatment follow-up visits on Day 344 (± 7) and Day 372 (± 7).

- Subjects who are not eligible for (or who choose not to participate in) the OLE period will be followed for approximately 8 weeks after the last dose per the Schedule of Events ([Table 1](#)). The Follow-Up Period includes the Day 169 (± 7) visit (4 weeks after the last dose) and the Day 197 (± 7) visit (8 weeks after the last dose).
- If absolute lymphocyte and/or eosinophil counts have not recovered by the Day 197 visit (or the Day 372 visit for subjects participating in the OLE period), subjects will return approximately every 28 days for extended follow-up until counts have recovered.
- Total study duration is approximately 33–36 weeks or 58–61 weeks for subjects participating in the OLE period, though the study duration could be extended for monitoring absolute lymphocyte and/or eosinophil counts (as described above).

5.2 Schedule of Events

The schedule of procedures and assessments (excluding the OLE period) is depicted in [Table 1](#). The OLE schedule of procedures and assessments is depicted in [Table 5](#) (Section [19.12.5](#)).

Table 1 AK002-014 Schedule of Events

Description	Baseline/ Screening ² (14–60 days)	Dose 1 Day 1 ²	Day 8 (±1 day)	Day 15 (±2 days)	Dose 2 Day 29 (±3 days) ³⁵	Dose 3 Day 57 (±3 days) ³⁵	Dose 4 Day 85 (±3 days) ³⁵	Dose 5 Day 113 (±3 days) ³⁵	Dose 6 Day 141 (±3 days) ³⁵	Day 169 (±3 days) ³⁵ (or ET ³²)	EOS Day 197 (±7 days)	Extended Follow-Up ³³
Informed consent	X											
Demographics and Medical History	X											
Stool for Ova and Parasite ³	X											
ePRO Activation and Training ⁴	X											
DSQ PRO ⁵	Daily from Screening through End of Study (or ET) ----->											
CCI	X			X	X							
EG/EoD PRO Questionnaire ⁷	X											
CCI	X	X ¹			X ¹	X ¹	X ¹	X ¹	X ¹	X ¹	X ¹	
Baseline Diet Assessment ⁹	X											
Baseline Diet Compliance ⁹		X ¹		X	X ¹	X ¹	X ¹	X ¹	X ¹	X	X	
Body Weight and Height ¹⁰	X	X ¹			X ¹	X ¹	X ¹	X ¹	X ¹	X	X	
Vital Signs ¹¹	X	X ¹		X	X ¹	X ¹	X ¹	X ¹	X ¹	X	X	
10 or 12-Lead ECG ¹²	X											
Complete Physical Examination ¹³	X											
EGD with Biopsy Collection ¹⁴	X									X		
EREFS Scoring during EGD ¹⁵	X									X		
Blood for Serology ^{16,17}	X											
Blood for Serum hCG and FSH ^{16,18}	X											
Blood for Total Serum IgE ^{16,19}		X ¹					X ¹			X		
Blood for CBC w/Differential ^{16,20}	X	X ¹	X	X	X ¹	X ¹	X ¹	X ¹	X ¹	X	X	X
Blood for Chemistry ^{16,21}	X	X ¹			X ¹	X ¹	X ¹	X ¹	X ¹	X	X	
Blood for PK ^{16,22}		X ¹	X	X	X ¹	X ¹	X ¹	X ¹	X ¹	X	X	
Blood for ADA ^{16,23}		X ¹			X ¹	X ¹	X ¹	X ¹	X ¹		X	
Blood for Exploratory Analysis ^{16,24}	X			X						X	X	
Blood for Exploratory Safety ^{16,25}		X ¹			X ¹	X ¹	X ¹	X ¹	X ¹			

Table 1 AK002-014 Schedule of Events cont.

Description	Baseline/ Screening ² (14-60 days)	Dose 1 Day 1 ²	Day 8 (±1 day)	Day 15 (±2 days)	Dose 2 Day 29 (±3 days) ³⁵	Dose 3 Day 57 (±3 days) ³⁵	Dose 4 Day 85 (±3 days) ³⁵	Dose 5 Day 113 (±3 days) ³⁵	Dose 6 Day 141 (±3 days) ³⁵	Day 169 (±3 days) ³⁵ (or ET ³²)	EOS Day 197 (±7 days)	Extended Follow-Up ³³
Urine for Urinalysis ^{16,26}	X	X ¹		X ¹	X ¹	X ¹	X ¹	X ¹	X ¹	X ¹	X ¹	
Eligibility Assessment	X	X ¹										
Premedication – prednisone ²⁸	X ¹											
Urine Dipstick Pregnancy Test ^{16,27}		X ¹			X ¹	X ¹	X ¹	X ¹	X ¹			
Access IRT – IP Kit Assignment		X ¹			X ¹	X ¹	X ¹	X ¹	X ¹			
Study Drug Administration ²⁹		X			X	X	X	X	X			
Post-Dose Observation ²⁹		X			X	X	X	X	X			
Symptom-Directed Physical Exam ³⁰		X ¹		X ¹	X ¹	X ¹	X ¹	X ¹	X ¹	X ¹	X ¹	
Prior and Concomitant Medications	X	X	X	X	X	X	X	X	X	X ³⁴	X	
Adverse Events ³¹	X	X	X	X	X	X	X	X	X	X	X	X
Open-Label Extended Dosing ³⁴										X ³⁴	X ³⁴ – Day 197 visit does not apply to subjects in OLE period	

ADA: Anti-drug Antibody

ET: Early Termination

FSH: Follicle-Stimulating Hormone

IP: Investigational Product

CBC: Complete Blood Count

ECG: Electrocardiogram

hCG: Human Chorionic Gonadotropin

PK: Pharmacokinetics

DSQ: Dysphagia Symptom Questionnaire

EGD: Esophago-gastro-duodenoscopy

IRT: Interactive Response Technology

Table 1 Notes

- 1) Refer to assessment footnote for specific time points (e.g., predose, during infusion, postdose) to conduct the assessment on dosing days.
- 2) The screening period (Baseline) assessments can be conducted over multiple days within the screening period. The screening period must be a minimum of 14 days (2 weeks) and no longer than 60 days (or a maximum of 35 days after the Screening EGD, whichever is shorter). Day 1 can begin as soon as eligibility criteria are met.
- 3) Fecal collection kits for Ova and Parasite will be provided to subjects at the time of consent. Stool sample should be returned to the clinical site within 24 hours of collection.
- 4) At the time of consent, the Study Coordinator will activate all ePRO questionnaires in EDC, provide the subject with a unique username and password, train the subject on daily DSQ ePRO completion and compliance, and ensure the subject is able to complete the **CCI** questionnaire on their personal electronic device while on site.
- 5) Subjects should complete the DSQ daily after the last meal of the day. If Question 1 is answered “No,” the subject should answer the Solid Food Question ([Appendix 2](#)) after the DSQ is completed and submitted. The site is responsible for monitoring compliance throughout the duration of the study and discussing compliance during study visits.

Table 1 Notes cont.

- 6) On Day -2 (2 days before Day 1), on Day 15 (approximately 2 weeks after the first dose), and on Day 29 (approximately 4 weeks after the first dose), subjects will self-administer the CCI [REDACTED] after they submit the DSQ (and Solid Food Question, if applicable). On Day 15 and Day 29, subjects will also self-administer the CCI [REDACTED] after the DSQ, Solid Food Question (if applicable), and CCI [REDACTED].
- 7) During the screening period only, subjects should complete the EG/EoD PRO questionnaire daily after completion of the DSQ (and Solid Food Question, if applicable).
- 8) The CCI [REDACTED] electronic questionnaire should be the first assessment completed by the subject at the beginning of the study visit prior to all other study visit assessments.
- 9) A baseline diet assessment will be performed using the standardized questions in [Appendix 7](#). Eating patterns, food avoidance behaviors, and allergies will be captured. Per Inclusion Criteria #7, subjects should maintain baseline diet throughout the study. Diet compliance will be discussed during study visits, and any variance will be documented.
- 10) Height (in cm) and weight (in kg) will be measured at screening. Weight will also be measured predose on Days 1, 29, 57, 85, 113, 141, and on Days 169 and 197 (or ET).
- 11) Vital signs will be measured at baseline and on Days 1, 15, 29, 57, 85, 113, 141, 169, and 197 (or ET). On dosing days (Days 1, 29, 57, 85, 113, and 141), vital signs will be measured predose, 15 minutes (± 5 minutes) after infusion start, immediately postdose (within 5 minutes after infusion end), and 1 hour (± 5 minutes) postdose. Subject should be at rest for ≥ 5 minutes before vital signs (systolic and diastolic blood pressure, pulse, body temperature, and respiratory rate) are measured.
- 12) Baseline ECG should be performed after the subject has been in the supine position for ≥ 5 minutes and, if done on the same day as blood collection, do before blood is drawn.
- 13) A complete physical examination will be performed by either the Investigator or designee and include the following body system or organ assessments: skin; head, eyes, ears, nose, and throat; thyroid; lungs; cardiovascular; abdomen; extremities; lymph nodes; and a brief neurological examination.
- 14) An EGD with biopsy collection will be performed during screening and at Day 169 (± 3 days). EGD biopsies will be collected, processed, and shipped in accordance with [Appendix 9](#), the lab manual, and the histology manual. Day 169 biopsy results will be blinded. If ET occurs after Day 29 and before Day 169, an EGD with biopsy collection should be done 28 (± 3) days after the last dose (as part of the ET visit, see [Table Note 32](#)). If rescue therapy is required, an EGD (biopsy and EREFS) must be done prior to initiation of rescue medication or at the time of emergency dilation (instead of at Day 169).
- 15) During the Screening EGD and Day 169 EGD, severity will be evaluated using the EoE Reference Score for Endoscopic Abnormalities per the study histology manual.
- 16) Please see the study central laboratory manual for collection, processing, and shipment instructions. If possible, samples should be shipped on the same day as collection.
- 17) Blood for serology (Hepatitis B surface antigen, Hepatitis C antibody, Hepatitis B core antibody, and HIV) will be obtained during screening.
- 18) For female subjects, blood will be obtained during screening to test for hCG (pregnancy) and FSH (post-menopausal status).
- 19) Blood for total serum IgE will be obtained on Days 1 (predose), 85 (predose), and 169 or ET, if subject early terminates before Day 169.
- 20) Blood for CBC with differential will be obtained at all study visits. On Days 1, 29, 57, 85, 113, and 141, blood will be drawn twice (predose and 1-hour postdose). For every CBC with differential blood collection except screening and Day 1 (predose), the blood count results will be blinded to the Sponsor and the site. The safety monitor may request an unscheduled CBC with differential. Blood counts from Day 197 will be used to determine if extended follow-up is needed.
- 21) Blood for chemistry will be obtained during screening, predose on dosing days (Days 1, 29, 57, 85, 113, 141), and on Days 169 and 197 (or ET).

Table 1 Notes cont.

- 22) Blood for PK will be obtained on Days 1, 8, 15, 29, 57, 85, 113, 141, 169, and 197 (or ET). Blood will be drawn predose on Days 1, 29, 57, 85, 113, and 141.
- 23) Blood for ADA will be obtained predose on Days 1, 29, 57, 85, 113, and 141, on Day 197 (or ET), and in the event of a suspected immunogenicity-related AE.
- 24) Blood for exploratory analysis will be obtained during screening and on Days 15, 169, and 197 (or ET).
- 25) If an infusion-related reaction results in infusion interruption or cessation, blood for exploratory safety analyses will be obtained within 1–2 hours of symptom onset.
- 26) Urine for standard urinalysis will be obtained during screening, as needed (if warranted in the opinion of the Investigator or Subinvestigator), and on Day 197 (or ET).
- 27) For females of childbearing potential, urine for dipstick pregnancy test will be collected, tested, and results confirmed predose on Days 1, 29, 57, 85, 113, and 141.
- 28) The day before the first dose (12–24 hours prior to the planned infusion start time), eligible subjects will self-administer oral prednisone premedication based on body weight.
- 29) Study drug (or placebo) will be administered as a single peripheral IV infusion over ≥ 4 hours on Day 1, over ≥ 3 hours on Day 29, and over ≥ 2 hours for subsequent infusions (Days 57, 85, 113, and 141). Refer to the Pharmacy Manual for detailed instructions on preparation, administration, and infusion rate schedule requirements.
- 30) If a new or worsening symptom (or clinically significant finding) is observed or reported, the Investigator or designee will perform a symptom-directed physical examination. Symptom-directed physical examinations will be performed as needed and may be performed predose, during infusion, and/or postdose (including for possible IRRs).
- 31) All AE, including Adverse Events of Special Interest (AESI) and SAE, will be captured beginning from the start of the first infusion. Serious adverse events occurring between the time of consent and the start of the first study drug infusion will be reported only if they are assessed to be related to study procedures. For subjects participating in the OLE period, AE will be assessed and recorded in the CRF of the AK002-014 treatment period database up until the start of the first open-label infusion during the Day 176 visit and recorded in the CRF of the AK002-014 OLE period database beginning from the start of the first open-label infusion during the Day 176 visit.
- 32) ET visits should be conducted 28 (± 3) days after the last dose of study drug or prior to this, if necessary, to ensure compliance with the visit. If a subject discontinues the study > 28 days after the last dose of study drug, the ET visit should be conducted as soon as possible. If the subject is terminated after Day 29 and before Day 169, the ET visit will be performed 28 (± 3) days after last dose and the ET visit will follow the Day 169 assessment schedule (including EGD with biopsy collection). If the subject is not participating in the OLE period and the ET visit occurs after Day 169, the Day 197 assessment schedule should be followed for the ET visit. See [Table 5](#) OLE Period Schedule of Events for OLE period ET after Day 176.
- 33) If absolute lymphocyte and/or eosinophil counts do not recover (to normal range or baseline levels) by Day 197 (or ET), extended follow-up visits are required every 28 (± 3) days) to monitor blood counts until they recover. Extended follow-up visits consist of blood collection for CBC with differential and collection of AESI and SAE.
- 34) After completion of the Day 169 visit, the Investigator will evaluate whether the subject is eligible for the OLE period. If the subject is eligible, the subject will be given the option to participate in the OLE period beginning approximately 1 week after the Day 169 visit. Approximately 1 week after the Day 169 visit (on Day 176 ± 3 days), eligible subjects that choose to participate in the OLE period will begin following the OLE Schedule of Events (Table 5) and will receive the first open-label AK002 infusion. For subjects participating in the OLE period, AE and concomitant medications should be collected and recorded in the AK002-014 Treatment Period database up until the start of the first open-label infusion during the Day 176 visit. This includes prednisone premedication administered prior to the Day 176 visit of the OLE period, which should be recorded in the Concomitant Medications CRF of both the AK002-014 treatment period database and the AK002-014 OLE period database.
- 35) Sites should strive to conduct visits within a ± 3 day window, but visits conducted within ± 7 days are acceptable and are not considered deviations. Visits conducted ± 4 -7 days from the target visit date should be minimized as much as possible. Any visit conducted outside of the ± 3 day window should receive prior written approval from Allakos.

6. Criteria for Evaluation

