2.3 Overview of Clinical Studies

AK002, administered as a monthly intravenous infusion, has previously been tested in healthy volunteers and in subjects with indolent systemic mastocytosis (ISM), chronic urticaria, severe allergic conjunctivitis (AC), mast cell gastritis, and eosinophilic gastritis (EG) and/or eosinophilic duodenitis (EoD), referred to as eosinophilic gastroenteritis (EGE) in previous studies.

Multiple doses of 3 mg/kg have been given to subjects with ISM, chronic urticaria, severe AC, mast cell gastritis, and EG and/or EoD. In these studies, AK002 pharmacodynamic (PD) activity was observed for prolonged periods of time and the AK002 pharmacokinetic (PK) parameters demonstrated a half-life amenable to administration every 4 weeks.

To date, 51 healthy volunteers (36 on AK002, 15 on placebo), 25 subjects with ISM, 47 subjects with chronic urticaria (including spontaneous and inducible), 30 subjects with severe AC, 8 subjects with mast cell gastritis, and 65 subjects with EG and/or EoD (43 on AK002 and 22 on placebo) have been enrolled in clinical studies.

In general, AK002 was well tolerated. The most common treatment-emergent adverse event (TEAE) observed was infusion-related reactions (IRR). Most IRR were mild to moderate and 2 IRR (1 in the healthy volunteer study and 1 in the AK002-003 study) were serious but resolved within 24 hours. Common symptoms of IRR were headache, nausea, sweating, flushing, and redness. Most IRR occurring during the infusion could be managed by slowing or temporary interruption of the infusion, with minimal intervention. In 6 healthy volunteers who received 2 doses of 0.3 mg/kg, 4 weeks apart, the second dose was better tolerated than the first dose. This is also the case in patients with ISM, chronic urticaria, severe AC, and EG and/or EoD; fewer adverse events (AE) were reported during the second and subsequent infusions when compared to the first infusion.

In all studies, a transient decrease in lymphocyte counts was observed after the AK002 infusion (usually resolving within 1 day) that was not associated with any clinical consequence, and a sustained depletion of eosinophils was observed that is consistent with the mechanism of action of AK002. No significant trends were observed for changes in vital signs, electrocardiograms (ECG), clinical laboratory parameters, or physical examinations.

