10.3 Blinding

The identity of test and control treatments will not be known to Investigators, Sponsor, research staff, subjects, or the primary study monitor.

The following study procedures will be in place to ensure double-blind administration of study treatments:

- Access to the randomization codes will be strictly controlled via the IRT system.
- Throughout the study, the blind should remain unbroken except for an emergency when knowledge of a subject's study medication is necessary for further management or if required for regulatory reporting. The Allakos Medical Monitor approves any emergency blind break, if at all possible, prior to the unblinding.
- Study drug vial labels will be blinded, and AK002 and placebo for infusion will be identical in appearance.
- Results from analysis of blood samples for PK and ADA will not be provided to the Investigator and Sponsor until after final database lock.
- Results from analysis of blood samples for exploratory analysis or exploratory safety analysis (unless immediately required for safety issues) will not be provided to the Investigator and/or Sponsor until after final database lock of the double-blind portion of the study.
- For time points occurring after the initial infusion of study drug during the double-blind portion of the study, results of the following assessments will not be provided to the Investigator and/or Sponsor until after final database lock. The results will be reviewed on an ongoing basis by the Safety Monitor and escalated as appropriate.
 - Differential cell counts (including neutrophils, eosinophils, basophils, monocytes, and lymphocytes) from peripheral blood.
 - Enumeration of eosinophils and ^{CCI} [REDACTED] from Day 169 EGD biopsies.

Other than for the conditions described above, the study blind will be revealed after all subjects have completed their participation in the double-blind portion of the study and the database for the double-blind portion of the study has been locked.

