11.2.8 Complete Blood Count with Differential

Blood for CBC with differential will be obtained at all study visits. On dosing days (Days 1, 29, 57, 85, 113, and 141), blood for CBC with differential will be drawn twice: predose and 1 hour postdose.

The blood sample will be processed and shipped in accordance with the central laboratory manual and lab kit instructions. The central laboratory will analyze the blood sample and provide results for CBC with differential, including hemoglobin, hematocrit, platelet count, red blood cell count, white blood cell count, and absolute differential count (neutrophils, lymphocytes, monocytes, eosinophils, and basophils).

As described in the Investigator's Brochure, expected effects of AK002 include changes in absolute lymphocyte and eosinophil counts, so these results could potentially unblind the blinded members of the study. Consequently, with the exception of screening and Day 1 predose, the CBC differential results (neutrophils, lymphocytes, monocytes, eosinophils, and basophils) will be blinded to both the Sponsor and the study site. The CBC differential results for Day 1 (1 hour postdose), Days 8, 15, 29, 57, 85, 113, 141, 169, and 197 (or ET) will therefore be unavailable during the study and will not be provided to the Sponsor or study site until after final database lock and unblinding.

The Safety Monitor will have real-time access to these laboratory results and will review and escalate any concerns/issues to the Medical Monitor and/or the site as appropriate. An unscheduled CBC, with differential may be collected if requested by the Safety Monitor. All panic alerts for blinded values will be sent to the Safety Monitor and evaluated in real time.

If the CBC differential results from Day 197 (or ET) show that absolute lymphocyte and/or eosinophil counts have not recovered (to normal range or baseline levels), the subject must return for Extended Follow-Up visits approximately every 28 days to monitor blood counts until lymphocyte and/or eosinophil counts have recovered. Extended Follow-Up visits will consist only of blood collection for CBC with differential and collection of any AESI and SAE.

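### The schedule note masks all blood count results after Day 1 predose, but Sections 10.3 and 11.2.8 mask only the differential, so total white cell count is left as a possible unblinding route of unknown strength

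*Protocol*

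**What the plan says.** Three places in the protocol define which blood counts are hidden from site and Sponsor.

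- **Table 1 note 20 (Section 5.2; repeated in SAP Section 3.2).** Apart from screening and Day 1 predose, "the blood count results will be blinded to the Sponsor and the site". No component is singled out. The same note requires two draws on each of the six dosing days, one before the infusion and one an hour after it.
- **Section 10.3, Blinding.** The peripheral blood item withheld after the first infusion is "Differential cell counts (including neutrophils, eosinophils, basophils, monocytes, and lymphocytes) from peripheral blood". Total WBC is not named.
- **Section 11.2.8.** The central laboratory reports "hemoglobin, hematocrit, platelet count, red blood cell count, white blood cell count, and absolute differential count", so WBC is an item apart from the differential. The section then says "the CBC differential results (neutrophils, lymphocytes, monocytes, eosinophils, and basophils) will be blinded to both the Sponsor and the study site". The reason given is that "expected effects of AK002 include changes in absolute lymphocyte and eosinophil counts, so these results could potentially unblind the blinded members of the study".

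Section 2.3 reports a short-lived lymphocyte fall after infusion in all earlier studies, usually over within a day, and a sustained eosinophil depletion. SAP Section 3.4 states the double-blind principle but lists no laboratory items.

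**The concern.** A central laboratory cannot set up its reports to satisfy both wordings. Under note 20, WBC is masked; under Sections 10.3 and 11.2.8 it is not. WBC is the sum of the differential counts, so it carries part of the signal that the masking is meant to hide. The paired draws make each subject his or her own control up to six times. The site also sees the differential at screening and Day 1 predose, so it knows how much of the starting total was lymphocytes and eosinophils.

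Several assessments depend on a site that does not know the arm. The attending physician grades EREFS (Section 11.2.7.1), a secondary endpoint at positions 6 and 13 of the testing order (SAP Table 7). The investigator judges adverse event causality (Section 13.6.3). Rescue therapy is given on medical need (Section 8.1), and rescue use is listed as an intercurrent event (SAP Section 4.2.4). The second co-primary endpoint is reported by subjects whose diary compliance site staff discuss at visits.

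**Working it through.** **Comparing the texts.** The plan has no figure to reproduce here; the finding rests on scope.

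| Item after Day 1 predose | Note 20 | 10.3 | 11.2.8 |
|---|---|---|---|
| Five differential counts | masked | masked | masked |
| Total WBC | masked | not listed | reported, not listed as masked |
| Hemoglobin, hematocrit, red cells, platelets | masked | not listed | reported, not listed as masked |

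Note 20 applies to every later sample, including predose draws from Day 29 and non-dosing visits, not only to postdose draws.

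**How informative could WBC be?** The documents give none of the inputs, so this is an illustration on assumptions:

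- lymphocytes plus eosinophils make up 20–40% of WBC;
- they fall 30–80% by the 1-hour draw on AK002;
- other cells do not change, and WBC does not change on placebo;
- the SD of the same-day change in WBC is 10–20 percentage points in both arms;
- the fall is the same at each infusion and pairs are independent.

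Fall in WBC = share × fractional fall: from 0.20 × 0.30 = 6% to 0.40 × 0.80 = 32%.

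For the mean of k pairs, AUC = Φ( [fall ÷ (SD/√k)] ÷ √2 ).

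Lowest case, one pair: 0.06/0.20 = 0.30; 0.30/1.414 = 0.212; Φ = 0.584. Highest case, one pair: 0.32/0.10 = 3.2; 3.2/1.414 = 2.263; Φ = 0.988.

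| Share | Fall in those cells | WBC fall | SD 10, 1 pair | SD 10, 6 pairs | SD 20, 1 pair | SD 20, 6 pairs |
|---|---|---|---|---|---|---|
| 0.20 | 0.30 | 6% | 0.664 | 0.851 | 0.584 | 0.698 |
| 0.30 | 0.50 | 15% | 0.856 | 0.995 | 0.702 | 0.903 |
| 0.40 | 0.50 | 20% | 0.921 | 1.000 | 0.760 | 0.958 |
| 0.40 | 0.80 | 32% | 0.988 | 1.000 | 0.871 | 0.997 |

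**Prednisone.** All subjects, placebo included, take 40–80 mg the day before dose 1 only (Section 9.6). If that makes the first pair unusable, five remain. For a 6% fall with SD 20: 0.06/(0.20/√5) = 0.671; 0.671/1.414 = 0.474; AUC about 0.68. With SD 10 it is about 0.83. For a 15% fall the five-pair values are about 0.88 and 0.99.

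**Timing.** Six pairs exist only from Day 141, which is 28 days before the Day 169 endoscopy. Earlier decisions would rest on fewer pairs.

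**The case against.** The strongest reply is that no leak is documented. Nowhere do the documents say that sites receive WBC; note 20 read literally prevents it, and the central laboratory manual, which is not available here, may settle the matter. No rule ranks Sections 10.3 and 11.2.8 above the schedule note. This stands: the narrower text permits release but does not state it.

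A second reply is that the texts may not conflict. Table 1 note 33 uses blood counts as shorthand for lymphocyte and eosinophil counts, and note 20 could be read the same way. That would remove the contradiction, but WBC would then be unmasked everywhere, so the gap would remain.

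A reader might infer that the 1-hour draw catches the known lymphocyte fall. The documents do not support that: Section 2.3 places the fall after infusion and usually over within a day, with no 1-hour figure, no size, and no mention of total WBC. A reader might also take the AUCs above 0.9 as expected performance. They rest wholly on assumed inputs, and the six-pair values also suppose that someone averages every pair. A neutrophil rise would lower them.

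The reach is also limited. Histology is read by a blinded central reader (Section 11.2.7.2), and the DSQ is self-completed and cannot be edited after entry (Section 11.2.1). Infusion reactions, the most common adverse event in earlier studies, are already visible to sites; what WBC would add to them is not known.

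**Conclusion.** The inconsistency in wording is real and should be corrected. Under Sections 10.3 and 11.2.8, total WBC is left unmasked although it includes the two cell types the protocol itself regards as potentially unblinding. The strength of the leak cannot be established from the documents. On the stated assumptions, discrimination from a single pair runs from an AUC of about 0.58 to 0.99, and from six pairs from about 0.70 to near 1.00.

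It would go too far to conclude that sites were shown WBC or that the blind was broken. The supportable conclusion is that a potential route is open under one of two conflicting rules. It bears most on the locally graded EREFS, causality judgments and rescue decisions, and only indirectly on the co-primary endpoints. Because closing it is cheap, the uncertainty about its size is not a reason to leave it.

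**What to change.** Write one masked list and use it word for word in Table 1 note 20 (protocol and SAP), Section 10.3 and Section 11.2.8:

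- total WBC and the five differential counts are withheld from site and Sponsor for every double-blind sample after Day 1 predose, until the planned unblinding;
- an explicit statement of whether hemoglobin, hematocrit, red cells and platelets are masked, since note 20 as written covers them and the other two sections do not;
- the same rule for CBCs run locally, where feasible, because Section 11.4 allows local testing during the pandemic and extra investigator-ordered tests, which a central laboratory setting would not reach;
- the Safety Monitor's real-time access, and panic alerts for all masked values, kept as Section 11.2.8 already provides.

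The cost is wording in two documents, a change to the central laboratory report, and an instruction to sites on local counts. The downside is that sites do not see WBC in real time; the existing Safety Monitor route covers this.
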